# 1. BACKGROUND

# 1.1 PATHOPHYSIOLOGY

Diabetic macular edema (DME) is the most common cause of vision loss from diabetic retinopathy. It is characterized by macular swelling secondary to increased vascular permeability secondary to loss of pericytes in the macular vascular bed. Clinically, microaneurysms and exudates are often seen in association with macular edema. Foveal-involving cystic changes and macular edema can have significant impact on visual loss. Extent of perfusion and ischemia also is important for visual prognosis.

Multiple factors play a role in the evolution of diabetic macular edema. Vascular endothelial growth factor has been shown to be significantly elevated in diabetic retinopathy and may play an important role in the evolution and pathogenesis of DME. Increasing VEGF levels are also seen in the setting of progressive ischemia, such as proliferative diabetic retinopathy when extensive peripheral nonperfusion may be present. Reducing the active levels of VEGF may have significant positive consequences for outcomes related to DME management.

# 1.2 TREATMENT OF DIABETIC MACULAR EDEMA

Following the Early Treatment of Diabetic Retinopathy Study (ETDRS), focal/grid laser photocoagulation became the standard treatment for DME. This therapy may continue to have an important place in the treatment of macular edema. Utilizing laser photocoagulation, the ETDRS achieved stabilized vision for a significant number of patients with diabetic macular edema.

However, advances in pharmacotherapy have resulted in exciting new treatment modalities for DME. The Diabetic Retinopathy Clinical Research Network (DRCR.net) conducted a study comparing intravitreal triamcinolone to laser photocoagulation. In this study laser photocoagulation performed better over the long-term with reduced side effects. However, other studies have suggested that particularly in pseudophakic patients, steroids are an important treatment alternative. Long-lasting steroid delivery systems are also currently under investigation, including a dexamethasone implant and fluocinolone implant. Results from these studies are promising but at this time these

devices are still under investigation and are not FDA-approved in the United States.

Since the initial publication of the DRCR.net study that suggested superiority of ranibizumab to laser photocoagulation, VEGF inhibitors have become a first-line therapy for DME. Bevacizumab which is not approved for ophthalmic indications is among the most frequently used anti-VEGF agents. The BOLT study was a 2-year randomized controlled trial comparing bevacizumab to laser photocoagulation. Bevacizumab was given with a loading does every 6 weeks for three injections and then retreatment occurred every 6 weeks. Bevacizumab performed significantly better than the laser group with a median gain of 9 letters compared to 2.5 letters. Nearly 50% of eyes gained 2 lines or more compared to 7% of the laser group. Given the limited size of the bevacizumab studies, conclusions regarding safety remain difficult.

Alfibercept is also being studied in the treatment of DME. In comparison to laser photocoagulation, the various dosing regimens of aflibercept showed a 9.7-12.0 letter gain compared to -1.3 letters for the laser group. When examining eyes with 3 line gain or more, 23.8-45.5% of eyes treated with aflibercept compared to 11.4% for the laser group. Aflibercept remains investigational at this time for the treatment of DME.

Ranibizumab is the first and currently only VEGF inhibitor approved for the treatment of DME. The results of the RISE/RIDE trials showed that 33.6 to 44.8% of eyes gained more than 3 lines at 2 years compared to 12.3-18.3% of sham eyes. Laser photocoagulation was allowed as a rescue therapy. Based on the results of the RISE/RIDE trials, the FDA approved ranibizumab 0.3 mg for the treatment of DME in August 2012.

#### 1.3 RANIBIZUMAB AND DIABETIC MACULAR EDEMA

As noted above, the pivotal RISE/RIDE phase III trials resulted in the FDA approval of ranibizumab for the treatment of DME. Numerous trials have suggested the efficacy and safety of ranibizumab in the treatment of DME, including the DRCR.net, READ, and RISE/RIDE. The results of these studies suggest that intravitreal ranibizumab therapy is a safe and effective

treatment modality for DME. Ranibizumab therapy results in functional stabilization in the vast majority of eyes and in significant improvement in nearly half of eyes. Additionally, RISE/RIDE revealed that eyes treated with ranibizumab had lower rates of retinopathy progression and higher rates of retinopathy improvement. In addition to the functional improvements, ranibizumab resulted in significant anatomic improvements with a mean reduction of ~ 250 microns in central foveal thickness compared to only 133 micron decrease in the laser group.

Prior to the approval of ranibizumab, bevacizumab was the only readily available VEGF inhibitor being utilized (off-label) for the treatment of DME. Although the functional results to bevacizumab therapy, appear promising, the systemic safety of bevacizumab for DME and the relative efficacy of bevacizumab compared to ranibizumab remain unknown. With ranibizumab's approval, it is unclear whether switching from bevacizumab to ranibizumab has a clinical impact on the disease course. Given the number of eyes treated with bevacizumab, answering this question is important. These questions are the focus of this investigation.

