# 4.1.2 Inclusion Criteria

Subjects will be eligible if the following criteria are met:

- Ability to provide written informed consent and comply with study assessments for the full duration of the study
- Age > 18 years
- ETDRS best-corrected visual acuity of 20/25 to 20/320 in the study eye
- Willing, committed, and able to return for ALL clinic visits and complete all study related procedures
- At least 6 previous bevacizumab injections for diabetic macular edema in the last 12 months.
- At least 2 bevacizumab injections within 10 weeks and the most recent bevacizumab injection within 6 weeks of baseline study visits
- Persistent foveal-involving diabetic macular edema based on presence of intraretinal and/or subretinal fluid by SDOCT in the foveal center at study entry

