# 4.3.2 Dosage, Administration, and Storage

#### a. Dosage

Subjects will be randomized to two equal size treatment groups. The first group will be treated with 0.3 mg ranbizumab monthly for the duration of the study. The second group will be treated with 0.3 mg monthly for the first three months and will subsequently be treated with 0.3 mg on a "treat-and-extend" protocol (as outlined in 4.3.2b).

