# 4.4 CONCOMITANT AND EXCLUDED THERAPIES

During the study period, no additional intravitreal or periocular pharmacologics can be administered, including but not limited to bevacizumab, aflibercept, and steroids. Focal laser photocoagulation is also not permitted during the study period. Panretinal photocoagulation is allowed if an eye develops retinal neovascularization, optic disc neovascularization, anterior segment neovascularization, and/or vitreous hemorrhage thought to be related to neovascularization.

Subjects may continue to receive all medications and standard treatments administered for their conditions at the discretion of their treating physician.

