REACT Study

Safety and Efficacy of Intravitreal Ranibizumab for Diabetic Macular Edema Previously Treated with Intravitreal Bevacizumab: A Randomized Dual-Arm Comparative Dosing Trial (Phase:1/2):

IND 120427

NCT01982435

Statistical Analysis Plan

11-07-2013

Measures for this study will be summarized using means, range and standard error of the means (SEM).

Two-sided paired t-tests and two-sided unpaired t-tests will respectively be conducted to analyze efficacy endpoints between study initiation to end, and between monthly and Treat and extend injection regimens. Patients who exit the study early can be accounted for by using a last observation carried forward approach. Chi-squared analysis will be used to assess significant differences in ophthalmic adverse event frequency. All analyses will be performed using GraphPad Prism 5 (GraphPad Software, La Jolla, California, USA) with a significance level of 0.05 being assumed for all tests

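### Section 1.3 sets out to learn the effect of switching and the relative efficacy of the two drugs, but every patient receives ranibizumab and the evidence on switching is uncontrolled within-patient comparison

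*Protocol*

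**What the plan says.** Protocol section 1.3 raises two questions about the drugs. On comparison it says that "the relative efficacy of bevacizumab compared to ranibizumab remain unknown"; on changing drug it says that "it is unclear whether switching from bevacizumab to ranibizumab has a clinical impact on the disease course". It then commits the trial to them: "These questions are the focus of this investigation". The opening of section 2 describes understanding effectiveness after previous anti-VEGF treatment as the primary objective, while section 2.1 gives the formal primary objective as adverse events.

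Section 4.3.2 assigns the same drug and dose to both arms. For Group 1: "The first group will be treated with 0.3 mg ranbizumab monthly for the duration of the study". For Group 2: "The second group will be treated with 0.3 mg monthly for the first three months", followed by treat-and-extend. Section 4.4 rules out bevacizumab during the study: "no additional intravitreal or periocular pharmacologics can be administered, including but not limited to bevacizumab, aflibercept, and steroids".

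Two planned analyses bear on switching.
- The SAP: "Two-sided paired t-tests and two-sided unpaired t-tests will respectively be conducted to analyze efficacy endpoints between study initiation to end", with the unpaired test used for monthly against treat-and-extend, all at the 0.05 level.
- Sections 3.3.2 and 4.8.3 and Appendix E: previous anatomic and functional anti-VEGF response, taken retrospectively from the medical record, is compared with response at months 3, 6 and 12. The SAP names no method specific to this comparison.

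On prior treatment, section 4.1.2 requires: "At least 6 previous bevacizumab injections for diabetic macular edema in the last 12 months".

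**The concern.** The effect of switching is a contrast between changing drug and staying on bevacizumab. No patient stays on bevacizumab, so that contrast is not observed. The randomised comparison is between two ranibizumab schedules and carries no information about one drug against the other.

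That leaves change within the same eye. Such change mixes the new drug with anything else that differs before and after entry: time, closer follow-up, a different injection frequency, and regression to the mean in eyes chosen because they were still wet. A significant paired t-test, set beside the wording of section 1.3, invites the conclusion that switching helped. Nothing in either document tells the reader that the analysis cannot support it.

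**Working it through.** **1. What each comparison can identify**

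| Comparison | Source | Differs between the sides | Identifies a drug effect? |
|---|---|---|---|
| Monthly vs treat-and-extend | SAP, unpaired t | Schedule only (randomised) | No; it identifies a schedule effect |
| Start vs end of study | SAP, paired t | Drug, time, frequency, selection | No |
| Prior response vs months 3, 6, 12 | 3.3.2, 4.8.3, App. E | The same, plus retrospective data | No |

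The third row has a further problem for vision. Prior acuity is Snellen (section 2.2), while on-study acuity is read on an electronic ETDRS chart (section 3.3.2).

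**2. Injection frequency**

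- Prior year: at least 6 (section 4.1.2).
- Group 1: months 0 to 11 in Appendix A = 12. For an eye at the entry minimum, 12/6 = 2.0 times.
- Group 2, extending at every visit under Criterion A of section 4.3.2 on nominal intervals: weeks 0, 4, 8, then +6, +8, +10, +12 = 14, 22, 32, 44. The next would be week 56. Total 7, and 7/6 = 1.17 times. If the first extension is instead decided at a week 12 visit, the sequence is 0, 4, 8, 12, 18, 26, 36, 48, a total of 8.
- Six is a floor. An eye with, say, 12 prior injections (an assumption) could fall to 7/12 = 0.58 times in Group 2.

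Frequency therefore changes along with the drug, by an amount and in a direction that depend on the eye and the arm.

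**3. Effect of any non-drug shift on the paired test**

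Let the shift be d standard deviations of the change. The two-sided paired t-test has noncentrality d√n. With no drug effect it rejects as follows:

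| d (assumed) | n = 30 | n = 15 |
|---|---|---|
| 0 | 5.0% | 5.0% |
| 0.2 | 18.5% | 11.2% |
| 0.3 | 35.5% | 19.2% |
| 0.5 | 75.4% | 43.8% |

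Both sizes are shown because the SAP does not say whether the arms are pooled. A concurrent 15 vs 15 comparison with the same shift in both arms stays at 4.8% to 4.9% (40,000 simulated trials, d = 0.3 and 0.5).

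**4. Regression to the mean**

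Three features point to it. Entry requires persistent foveal fluid (4.1.2). If both eyes qualify, the thicker becomes the study eye (4.1.1). Screening and baseline may be one visit (4.5.1, Appendix A), so the qualifying scan may itself be the baseline.

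Its size cannot be derived: the documents give no thickness distribution and no thickness threshold for entry. As an illustration only, assume selection on observed thickness above c = 300 or 350 µm, population mean µ = 350 to 450 µm, between-eye SD 80 µm, within-eye SD w = 40 or 60 µm, and no true change. Then

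s = √(80² + w²), r = 80²/s², z = (c − µ)/s, λ = φ(z)/(1 − Φ(z)), expected fall = (1 − r)·s·λ.

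- Largest (µ = 350, c = 350, w = 60): s = 100, r = 0.64, z = 0, λ = 0.798; fall = 0.36 × 100 × 0.798 = 28.7 µm. The SD of change is 79.8 µm, so d = 0.36. Rejection is about 47% at n = 30 (20,000 simulated trials).
- Smallest (µ = 450, c = 300, w = 40): s = 89.4, r = 0.80, z = −1.68, λ = 0.103; fall = 0.20 × 89.4 × 0.103 = 1.8 µm. Rejection is about 5.5%.

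Replacing the baseline by the mean of the qualifying scan and one earlier, unselected scan halves the fall, to 28.7/2 = 14.4 and 1.8/2 = 0.9 µm. Rejection is then about 5% to 19%.

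**5. Would a control arm help at this size?**

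With 15 per arm, power for a 0.5 SD difference is about 26% (noncentrality 0.5√(15/2) = 1.37, 28 df). The difference detectable with 80% power is about 1.06 SD. Detecting 0.5 SD needs 2(1.96 + 0.84)²/0.5² ≈ 63 per arm.

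**The case against.** The best defence is that section 1.3 is background. The formal primary objective is adverse events, and the listed secondary objectives are changes, proportions, injection counts and prior-response assessments. The study is a pilot with no formal sample size, and the SAP makes no drug-versus-drug claim. This stands as far as it goes: a reader might infer that a primary analysis fails, and the documents do not support that. It does not remove the problem, because section 1.3 makes the questions the trial's focus and the opening of section 2 puts effectiveness after prior anti-VEGF first.

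Three other stronger readings should be resisted.
- That the paired t-test is the only evidence. The prior-response comparisons are also planned and address switching more directly, though they too are uncontrolled.
- That injection frequency doubles at the switch. This holds only for a Group 1 eye at the entry minimum. Section 4.1.2 also requires at least 2 injections within 10 weeks and the latest within 6 weeks, and half the sample is in Group 2.
- That the test's true error rate is 5% to 47%. Entry is on fluid. The 300 µm figure in section 4.3.2 governs treatment intervals, and the result moves strongly with an assumed population mean.

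**Conclusion.** The concern holds as a mismatch between stated aim and design. The trial can describe outcomes after a switch to ranibizumab and can compare two ranibizumab schedules by randomisation. It cannot estimate the relative efficacy of the two drugs or the effect of switching. That conclusion rests on the documents alone and needs no numerical assumption.

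The size of the bias is not known. A non-drug shift of 0.2 to 0.5 SD would make the pooled paired test significant in 18.5% to 75.4% of trials with no drug effect, but those shifts are assumptions. The 2 to 29 µm range for regression to the mean comes from an entry rule that the trial does not use. Both show direction and possible scale, not a prediction.

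The point should be acted on, but it does not threaten the safety objective. Nor does it imply that a bevacizumab arm should be added: at 15 per arm such a comparison would have little power, so narrowing the claim is the remedy that fits.

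**What to change.** 1. Reword section 1.3, and add to section 2 and the SAP, that the paired and prior-response analyses describe outcomes after switching and do not estimate relative efficacy or the effect of switching. Keep causal wording for the randomised monthly versus treat-and-extend contrast.
2. Tabulate each arm's prior-year bevacizumab injection counts beside its on-study ranibizumab counts, so that the change in frequency is visible.
3. Where the records allow, repeat the thickness analysis with the mean of the last two pre-switch OCTs as baseline, labelled as a sensitivity analysis that reduces but does not remove regression to the mean. Section 3.1 promises only available imaging, so report how many eyes contribute.

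A subgroup of eyes with near-monthly prior dosing is not recommended. The documents do not define one, and it would split 30 eyes further.

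The cost is a weaker stated claim, one table and one extra analysis. Treatment history and OCT records are already reviewed under Appendix E, so no new patient contact is needed.

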# 1.4 NONCLINICAL EXPERIENCE WITH RANIBIZUMAB

#### 1.4.1 Nonclinical Pharmacokinetics

The pharmacokinetics of ranibizumab have been investigated in rabbits and cynomolgus monkeys following intravitreal and intravenous administration. In both species, following intravitreal administration, ranibizumab was cleared from the vitreous humor with a half-life of 2–3 days. Following single intravitreal administration to cynomolgus monkeys, retinal concentrations of ranibizumab were approximately one-third of vitreous concentrations and declined in parallel with vitreous concentrations. In humans, the intravitreal half-life of ranibizumab is estimated to be 9 days. Repeated intravitreal injections of ranibizumab can lead to detectable antibodies in serum in rabbits and cynomolgus monkeys.

# 1.4.2 Nonclinical Toxicology

A series of nonclinical studies of ranibizumab administered by intravitreal injection to cynomolgus monkeys have been performed (details regarding study design and results can be found in the Investigator Brochure).

#### 1.4.3 Nonclinical Data Supporting the Anti-Edema Activity of Ranibizumab

In Studies 01-401E-1757 and 01-401G-1757, the effect of ranibizumab on vascular leakage was explored using a modified Miles assay in the guinea pig. Ranibizumab demonstrated a concentration-dependent effect of blunting the vascular permeability induced by VEGF. These results are consistent with the decrease in retinal vascular permeability as observed on optical coherence tomography (OCT) and fluorescein angiography in AMD and diabetic macular edema studies and further support the rationale for the use of ranibizumab in CRVO and BRVO, in which vascular permeability plays a significant role in the pathology

# 1.5 CLINICAL EXPERIENCE WITH RANIBIZUMAB

Ranibizumab has been or is being studied in more than 5000 subjects with neovascular AMD, retinal vascular occlusive disease, and diabetic retinopathy/macular edema in a number of Phase I, I/II, II, III, and IIIb clinical trials. Ranibizumab is contraindicated in patients with ocular or periocular infections and in those with known hypersensitivity to ranibizumab or any of the excipients in ranibizumab. Intravitreal injections, including those with ranibizumab, have been associated with endophthalimits and retinal detachment. Proper aseptic injection technique should always be used when administering ranibizumab. Increases in IOP have been noted within 60 minutes of intravitreal injection with ranibizumab. Therefore, IOP as well as perfusion of the optic nerve head should be monitored and managed appropriately. Serious adverse events related to the injection procedure have occurred in <0.1% of intravitreal injections include endophthalmitis, rhegmatogenous retinal detachment, and iatrogenic traumatic cataract. Other serous ocular adverse events observed among ranibizumab-treated subjects and occurring in <2% of subjects included intraocular inflammation and increased IOP. The most common adverse reactions (reported > 6% higher in ranibizumab-treated subjects

than control subjects) were conjunctival hemorrhage, eye pain, vitreous floaters, increased IOP, and intraocular inflammation.

Although there was a low rate (<4%) of arterial thromboembolic events (ATEs) observed in the ranibizumab clinical trials there is a potential risk of ATEs following intravitreal use of inhibitors of VEGF. The rate of ATEs in three studies (FVF2598g, FVF2587g, and FVF3192g) in the first year was1.9% of subjects in the combined group of subjects treated with 0.3 mg or 0.5 mg ranibizumab compared with 1.1% of subjects in the control arms of the studies. In the second year of Study FVF2598g and FVF2587g, the rate of ATEs was 2.6% of subjects in the combined group of those treated with 0.3 mg or 0.5 mg ranibizumab compared with 2.9% of subjects in the control arm. The most common non-ocular adverse reactions observed in  $\geq$  15% of ranibizumab-treated subjects that occurred more frequently than in control subjects included, nasopharyngitis, headache, and upper respiratory tract infection.

The Sailor study (FVF3689g) evaluated the safety of intravitreal ranibizumab in a large population of subjects with CNV secondary to AMD. Subjects in Cohort 1 (N=2378) were randomized (1:1) to receive ranibizumab at a dose level of 0.3 mg or 0.5 mg; subjects were masked to these dose levels. Treatment was administered monthly for three initial doses (Day 0, Month 1, and Month 2), with scheduled follow-up visits on Months 3,6,9, and 12. Retreatment after the first three injections was performed as needed, on the basis of predefined criteria with injections no more frequently than every 30 days.

Cohort 2 (N=1992) consisted of subjects enrolled after the majority of Cohort 1 subjects had been enrolled, with enrollment continuing until ranibizumab was approved or denied by the FDA for US marketing, and if approved, until commercially available or 30 September 2006, whichever was earlier. Subjects in Cohort 2 received open-label ranibizumab at the 0.5 mg dose level, with an initial injection on Day 0 followed by retreatment at the physician's discretion, no more frequently than every 30 days. Subjects were monitored for safety for a total of 12 months; safety information, including both serious and nonserious adverse events, was collected at every clinic visit, with two formal safety visits scheduled at Months 6 and 12.

The study consisted of a 30-day screening period and a 1-year treatment period. Treatment duration was approximately 197 days for both dose groups in Cohort 1 and 144 days for subjects in Cohort 2. The mean follow-up time differed between Cohort 1 and Cohort 2, 337 days versus 254 days, respectively.

Ranibizumab was well tolerated, and the incidence of ocular SAEs and AEs was low and unrelated to dose. The rates of individual key ocular SAEs in Cohort 1 were < 1% and were similar across dose groups. Endophthalmitis or presumed endophthalmitis developed in 0.2% subjects in the 0.3-mg group and 0.4% subjects in the 0.5-mg group. The incidence of ocular inflammation, including iritis, uveitis, vitritis, and iridocylitis was 1.9% in the 0.3-mg group and 1.5% in the 0.5-mg group. Overall cataract rates were 5.4% (0.3 mg) and 6.0% (0.5 mg) and were similar when broken down by nuclear, subcapsular, and cortical subtypes. The rates of individual key ocular SAEs in Cohort 2 were <1%.

The rates of key non-ocular SAEs and AEs, including Antiplatelet Trialists' Collaboration (APTC) ATEs, MI, and vascular death were similar for cohorts 1 and 2 and 0.3- and 0.5-mg dose groups. The incidence of MI and non-ocular hemorrhage was similar across Cohort 1 dose groups. APTC ATEs, including vascular and unknown deaths, nonfatal MI, and nonfatal cardiovascular accidents, were similar across dose groups. During the 12-month study period, 0.7% of subjects in the 0.3-mg group and 1.2% of subjects in the 0.5-mg group suffered a stroke. The number of vascular deaths and deaths due to unknown cause did not differ across dose groups. Rates of key non-ocular SAEs in Cohort 2 were generally lower than those in Cohort 1.

Refer to the Ranibizumab Investigator Brochure or Lucentis® Package Insert for additional details regarding clinical safety experience with ranibizumab.

